1 PROTOCOL SUMMARY

1.1 SYNOPSIS

Title:	Cognitive Training Video Game to Target Subclinical Depressive Symptoms in Youth
Grant Number:	G028070
Study Description:	Youth with subclinical depressive symptoms (9-17) will be recruited to complete a cognitive training, video game-based, preventative intervention (CCT). Multilevel data (clinical measures of depression and anxiety symptoms and behavioral indexes of cognitive control capacity) will be collected before and after the intervention, to examine the extent to which CCT may reduce symptoms of depression and/or enhance cognitive control related behaviors.
Objectives:	
Primary Objective: To examine the efficacy of CCT in reducing depressive symptoms and improve cognitive control.
 
Secondary Objectives: To examine the durability of change in depressive symptoms and (if applicable) cognitive control 3-months after the CCT intervention.
 
Feasibility Objectives: 1) To assess whether participants engage in the intervention as instructed. 2) To assess whether participants enjoy engaging in the intervention. 3) To examine whether the effects of CBT in the Parent study have been maintained at a 2-year follow-up.

Endpoints:	
Primary Endpoints: Depressive symptoms and cognitive control behavioral performance after the intervention.
 
Secondary Endpoints: Depressive symptoms and cognitive control behavioral performance 3-months after the intervention. The secondary endpoint was discontinued as of protocol version 2.1 (02 April 2024).
 
Feasibility Endpoints: 1) Game-play metrics provided by Akili software; 2) ESS scores from each assessment; 3) Depressive symptoms at Assessment #1 of current study.

Study Population:	Anxious youth (AY) with subclinical depressive symptoms between the ages of 9 to 17.99
Phase or Stage:	N/A
Description of Sites/Facilities Enrolling Participants:	University of Michigan
Description of Study Intervention/Experimental Manipulation:	Participants will be recruited to complete the CCT intervention.
Study Duration:	Participants will be offered a 4-week, web-based cognitive control intervention (CCT), which is ~25 minutes a day x 5 days per week.
Participant Duration:	24 months
	Up to 6 months

1.2 SCHEMA

*Assessment 3 was optional to participants and then discontinued in protocol version 2.1 (02 April 2024).

1.3 SCHEDULE OF ACTIVITIES

	Pre-screening (Pre-consent)	Assessment 1 Day 1	Assessment 2 Day 60±30	Assessment 3** 150±20
Review eligibility with phone screen	X			
Informed Consent		X		
Demographics		X		
Clinical assessment				
CBCL		X		
MASC		X	X	X
CDI		X*	X	X
K-SADS (Clinical report)		X		
SCARED-P		X		X
CDSRS		X*	X	X
C-SSRS		X		
ERQ-CA		X	X	X
Behavioral assessment				
Millisecond Inquisit Web Cognitive Battery		X	X	X***
Other assessments				
ESS			X	X
Adherence Metrics from Akili			X	X
Debrief				X
Adverse Events Reporting		X	X	X

*These assessments may be administered more than once if >14 days pass before the cognitive battery and cognitive training can be administered. See Section 6.4 for additional details.

**Assessment 3 was optional to participants and then discontinued in protocol version 2.1 (02 April 2024).

***Provided iPads will be re-collected after Assessment 2. If participants do not have access to a personal tablet from which they can complete the tasks from, then they will not complete the Cognitive Battery at Assessment 3 (if applicable).

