If the Parent study does not yield sufficient participation, then we will recruit through the community using the social media campaign strategies that have proven effective in our past work, including UMHealthResearch. The proposed study will add up to three additional timepoints of assessment (pre-intervention, post-intervention, and (if applicable) 3-months post-intervention. All study activities will be completely remotely via an encrypted HIPAA-compliant video conferencing platform (e.g., Zoom), phone

call, and/or Qualtrics links. Depressive symptoms, anxiety symptoms, general psychopathology, and cognitive control behavior as indexed by a *Millisecond Inquisit Web* Cognitive Battery will be assessed pre-intervention. After the intervention, the same symptoms and cognitive control behavioral will be assessed. These variables will optionally be assessed again 3-months post intervention.

Data analyses will compare pre- and post-CCT data. Additionally, multilevel models will assess change in depressive symptoms and cognitive control over time and comparing between those who received CBT as compared to those who received RMT in the Parent study. These data will include *Millisecond* measures of behavioral capacity for cognitive control and detailed assessment of depressive and anxiety symptoms using both clinician-interview and self-report. Pre- to post-CCT change in depressive symptom severity (clinician-measured) will serve as the primary outcome variable.

At protocol version 2.1 (02 April 2024), Assessment #3 (3-month follow-up) was removed to increase feasibility so that resources could focused on increased recruitment.

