6.4 STUDY INTERVENTION/EXPERIMENTAL MANIPULATION ADHERENCE

Tolerability and compliance with the intervention will also be assessed. The CCT application will measure the amount of time each day that the child spends playing the video game. Additionally, completion of self-report questionnaires and *Millisecond* assessments will be tracked to ensure that these assessments are completed within the specified time period. If the cognitive task battery and start of the cognitive training intervention are not completed within sufficient time of the baseline clinical and self-report assessment (i.e., within 14 days of completing the CDI; due to scheduling and/or equipment constraints), then the CDI and CDRS-R will be re-administered prior to initiating the cognitive task battery and cognitive training.

Assessments will include (refer to 1.3 Schedule of Activities for a list of which measures are completed at each assessment):

Assessments by Clinician

- a) C-SRSS
- b) CDRS-R
- c) K-SADS

Assessments Completed by Subjects

- a) MASC
- b) CDI
- c) SCARED (parent)
- d) CBCL (parent)
- e) ERQ-CA

Other Assessments

- a) ESS (parent and child)

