8.2 SAFETY ASSESSMENTS

Safety assessments include the following:

- **Columbia Suicide Severity Rating Scale** (C-SSRS), Screen Version - Recent (Posner, Oquendo et al. 2007). A clinician-rated scale assessing suicidal ideation and behavior.
- **Child Depression Inventory** (CDI). A self-report assessment to rate the severity of depression symptoms in children. Total scores on this measure range from 0 to 54. Symptom worsening: > 25% increased CDI score (referenced to baseline).

Any safety-related assessments (C-SSRS administered at Assessment #1) or primary outcome measure (CDI at Assessments #1 or #2) that are missed will be reported to the IRB as a protocol deviation. We will accept a window of \pm 1 week. However, for the other assessments, missing or late assessments will not be reported as protocol deviations unless they constitute > 50% of the total assessments. These allowances should affect neither the scientific integrity nor the safety monitoring provisions of the protocol.

All SAEs will be:

- recorded on the appropriate SAE Report Form
- followed through resolution by a study clinician
- reviewed and evaluated by a study clinician.

The study will comply with IRB reporting requirements and guidelines for SAEs.

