9 STATISTICAL CONSIDERATIONS

9.1 STATISTICAL HYPOTHESES

Primary Endpoint:

We hypothesize that CCT will increase cognitive control capacity (Millisecond battery composite score and individual cognitive test scores) and reduce depressive symptoms (CDI and CDRS-R scores) over the 4 week period of the intervention. Specifically, we hypothesize that CCT will improve cognitive control which will in turn improve depressive symptoms as a consequence of enhanced emotional regulation. Alternatively, our null hypothesis is that there will be no difference in cognitive control capacity or depressive symptoms immediately post-intervention as compared to pre-intervention.

Secondary Endpoint*:

We hypothesize that CCT will further increase cognitive control capacity (measured by Millisecond battery composite score and individual cognitive test scores) and reduce depressive symptoms (as measured by CDI and CDRS-R) further 3-months post-intervention than immediately after the intervention. The null hypothesis is that there is no difference in cognitive control capacity or depressive symptoms from immediately post-intervention to 3-months after the intervention.

*Secondary endpoint was optional to participants and then discontinued after protocol version 2.1 (02 April 2024).

Feasibility/Acceptability and Experimental Endpoints:

1. We hypothesize that the majority of participants will complete the intervention with at least 80% compliance.
2. We hypothesize that participants will have favorable emotions associated with game play.
3. We hypothesize that depressive symptoms will be reduced from the baseline assessment of the Parent study but that they will be slightly elevated from the post-intervention assessment in the Parent study.

The statistical tests used to test these hypotheses will be outlined later in this protocol and registered with clinicaltrials.gov.

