9.4.6 PLANNED INTERIM ANALYSES

At Time 2, after the completion of the CCT intervention, CDI scores will be evaluated across all participants. If scores are significantly worse at Time 2 than at Time 1 (a significantly higher average CDI score across participants), then the study may be halted. Similarly, if greater than one third of the participants (~7 subjects) withdraw from the study due to symptoms, then the study may be halted. If there is no change, or an improvement in CDI scores (lower CDI scores), then the study will continue as planned. This interim analysis will be conducted with the intention of maintaining safety of participants, rather than for assessing the efficacy of the intervention.

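### Assessment 2, the primary post-measure, is timed from Assessment 1 and not from the end of training, so the lag after training can run from about 0 to 62 days

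*Combined protocol and SAP*

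**What the plan says.** Section 1.3 puts Assessment 1 on Day 1 and gives "Assessment 2 Day 60±30", that is, Days 30 to 90. Section 9.1 hypothesises change "over the 4 week period of the intervention" and states its null for outcomes "immediately post-intervention as compared to pre-intervention". Section 9.4.2 tests this with paired t-tests, before against after, with no term for time since training.

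Other sections fix the order of events but no interval. Section 4.1 says: "After the intervention, the same symptoms and cognitive control behavioral will be assessed". Section 9.4.6 says: "At Time 2, after the completion of the CCT intervention, CDI scores will be evaluated across all participants".

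The start of training can move. Under 6.4, if the battery and training do not begin within 14 days of the CDI, "then the CDI and CDRS-R will be re-administered prior to initiating the cognitive task battery and cognitive training". No latest start is given, and nothing says that Day 1 is reset. The end can move too, because 4.4 describes a completer as having had four weeks of training or more.

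Section 8.2 adds a second tolerance. It says that any "primary outcome measure (CDI at Assessments #1 or #2) that are missed will be reported to the IRB as a protocol deviation", and then: "We will accept a window of \pm 1 week". It names no date from which that week is counted.

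**The concern.** The hypothesis concerns the state of participants straight after a four-week course. The visit rule, followed as written, lets that measurement fall a few days after training for one participant and about two months after for another. With no control arm (6.3) and no time term, whatever happens to symptoms or task performance outside the training weeks is part of the estimated change.

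The protocol's own reasoning treats time since training as relevant: sections 3 and 9.1 expected further gains by three months. The follow-up that would have separated early from later change has been discontinued, so nothing else in the plan distinguishes them. Section 9.2 wants effect sizes for larger studies, and an effect size with an unspecified lag is harder to reuse.

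Two gaps add to this. Staff cannot tell whether ±30 days or ±1 week governs the CDI at Assessment 2. When baseline measures are repeated, two sets of scores exist and 9.4.2 does not choose between them.

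**Working it through.** **Inputs.** Assessment 1 is Day 1 and Assessment 2 falls on Days 30 to 90 (1.3). The course lasts 4 weeks, taken as 28 calendar days (4.1). A delay beyond 14 days triggers a repeat of the CDI and CDRS-R (6.4). Assumptions: the first CDI is on Day 1, and Day 1 does not reset.

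**Window in the plan.** 60 − 30 = Day 30; 60 + 30 = Day 90.

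**Lag.** If training starts on Day s, it ends on Day s + 27. A visit on Day v then has lag v − (s + 27). Over the window, the lag runs from 30 − s − 27 = 3 − s to 90 − s − 27 = 63 − s. Because the text places the visit after training, the lower end is taken as 0 where 3 − s is negative.

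| Start | End of course | Lag at Day 60 | Lag range, visit after training |
|---|---|---|---|
| Day 1 | Day 28 | +32 | +2 to +62 |
| Day 15 | Day 42 | +18 | 0 to +48 |

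Day 1 is the earliest possible start and gives the longest lags. Day 15 is the last start that needs no repeat CDI (15 − 1 = 14 days). From a Day 4 start onward, the window opens before the course ends (3 − 4 = −1), so only the ordering language keeps the visit after training. Counting from the last session of a 5-day week (Day s + 25) adds 2 days to the upper ends. A course longer than 28 days shortens them.

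**Untreated time in the contrast.** With the Day 1 CDI as baseline and the whole course inside the interval, the days outside training are v − 28, whatever the start day. A Day 60 visit gives 60 − 28 = 32 of 60 days. The start day decides only how those days split between before and after training.

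**If 8.2 means Day 60 ± 7 for the CDI** (an assumption; no anchor is stated), the window is Days 53 to 67. A Day 1 start gives 53 − 28 = +25 to 67 − 28 = +39. A Day 15 start gives 53 − 42 = +11 to 67 − 42 = +25. The narrower window reduces the spread, but the lag still depends on the start day.

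**Which baseline.** Take an assumed Day 29 start, with the CDI repeated that day and a Day 60 visit. The first CDI leaves 32 of 60 days outside training. The repeat spans 60 − 29 + 1 = 32 days, of which 32 − 28 = 4 lie outside.

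**The case against.** The strongest reply is that ±30 days is an outer scheduling envelope that works together with the rule that Assessment 2 follows training. That stands. A reader might infer from the day count alone that the plan permits the primary visit before training ends. Sections 2.3.1, 4.1, 4.2 and 9.4.6 all place it afterwards, so such visits are not claimed here. Removing them still leaves lags of about 0 to 62 days.

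A reader might also infer that Day 60 was meant as the nominal end of training, because Assessment 3 sat at Day 150 and 150 − 90 = 60. That is conjecture from a discontinued visit. It would equally fit counting three months from Assessment 2.

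On the baseline, the evident purpose of repeating the measures is to obtain a fresh score, so most analysts would use the repeat. That is the natural reading, and one sentence in 9.4.2 would settle it.

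Finally, this is an uncontrolled pilot, and the missing comparator is a larger limit than visit timing. That is also true. Timing and baseline are the parts that wording can repair.

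**Conclusion.** The point holds as a low-cost improvement. Assessment 2 is anchored to Assessment 1, the start of training is not capped, and the text gives no interval from the end of training. On a 28-day course with the visit after training, the lag can be +2 to +62 days for a Day 1 start and 0 to +48 days for a Day 15 start. The conclusion is limited to the text, since the schema figure in 1.2 is not shown.

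It does not follow that the primary estimate is biased by a known amount or in a known direction: the documents give no rate of change without treatment. Nor can it be said whether visits already completed are deviations. That depends on how the sponsor reconciles 1.3 with 8.2.

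The baseline question reaches beyond the CDI. Section 4.1 calls the clinician-measured change the primary outcome variable, 8.2 gives that role to the CDI, and both scales are repeated under 6.4. The definition of baseline must therefore cover both.

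**What to change.** 1. **Anchor.** In 1.3, replace Day 60±30 for Assessment 2 with one window that opens at each participant's end of training, of a width the sponsor can schedule. Make it the reference for the 8.2 tolerance at that visit, and bring 9.1 and 9.4.6 into line. Define end of training from the play log as the end of the assigned course: first recorded session plus 27 days, or the end of any extension documented by the study team. Ignore later play; otherwise one late session would move the anchor. The date then also exists for participants who stop training early but stay in the study (7.1). Those with under two weeks of training have no post-assessment under 5.5.
2. **Baseline.** In 9.4.2, define the *pre* value as the last CDI, CDRS-R and cognitive battery completed before the first training session.
3. **Reporting.** Report each participant's actual lag from end of training, and keep all completed visits in the primary analysis. A lag-adjusted analysis is optional and descriptive only, since lag may be confounded with adherence and scheduling.

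The cost is protocol wording and one derived variable from play data already recorded by day (6.4); visits are remote. The downside is tighter scheduling and possibly more deviations reported to the IRB, which is why the width is left to the sponsor.

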2 INTRODUCTION

2.1 STUDY RATIONALE

Rates of depression in children and adolescents are substantial (Basta et al., 2022), and prevalence is steadily increasing (Hawes et al., 2021). Challenges to the treatment of depressive disorders in youth include a dearth of trained providers, treatment cost, and imperfect treatment response with ~30%-60% failing to respond to gold standard treatments (TADS, 2004). These daunting challenges necessitate the development of preventative interventions to reduce subclinical depressive symptoms in children and adolescents *before* full-blown, clinical depression develops. Given links between depressive symptoms and low levels of cognitive control, video-game-based cognitive control training may serve as a low-cost, accessible, and suitable strategy for improving emotion regulation, lessening subclinical symptoms, and thereby reducing risk for developing clinical depression. The video-game intervention assessed in the current study is called *EndeavorRx*. Cognitive control training through *EndeavorRx* will target cognitive and affective domains, with the goal of improving cognitive control/emotion regulation and thus reducing depressive symptoms.

2.2 BACKGROUND

2.2.1 SUBCLINICAL DEPRESSION IS PREVALENT IN YOUTH, INCREASES RISK FOR FULL DEPRESSIVE DISORDER AND LONG-TERM IMPAIRMENT; BETTER INTERVENTIONS ARE NEEDED.

Depressive disorders are extremely common, beginning at peripuberty, with youth who experienced anxiety disorders at younger ages at especially high risk for depression in adolescence (Kessler et al., 2001; Basta et al., 2022). Despite the large number of youth experiencing these disorders a decade ago (~10% for depression and ~30% for anxiety; Merikangas et al., 2010), rates of depression and anxiety have continued to rise during the course of the COVID-19 pandemic (Hawes et al., 2021). Depression symptoms are often evident at young ages, and if left untreated, can lead to significant impairment in social, educational, and familial domains (e.g., school dropout, unemployment, social isolation, and suicide; Rapaport et al., 2005). Further, having symptoms of these disorders increases risk for developing additional psychopathology later in life. Despite treatments that exist to reduce symptoms of depression in youth, such as CBT, many children are left without care. Hospitals and clinics are overwhelmed with demand, and treatments like CBT are resource-intensive, putting a significant time-burden on patients, their families, and the clinicians (Rasing et al., 2017). There are not enough providers or resources to reach all the children and adolescents with depression and/or anxiety, even when considering that many youth and their families will not seek treatment in the first place (Planey et al., 2019; Reinert et al., 2021). Moreover, once a depressive disorder sets in, full remission following treatment is difficult to achieve, and as many as ~30-60% continue to experience clinically significant symptoms even after receiving treatment (TADS, 2004).

Prior research on youth depression has focused mostly on patients with diagnosed, clinical depression. However, depressive symptoms also exist at the subclinical level. For instance, estimates indicate that more than 20% of adolescents experience subclinical depressive symptoms (Wickrama et al., 2009); these youth have symptoms of depression but do not meet the diagnostic criteria that would indicate a full clinical diagnosis. Although youth who are suffering from subclinical symptoms are often absent from published prevalence estimates of depression, their impact on society and the healthcare system is hardly invisible. A recent study in Dutch youth found that the associated costs of *subclinical* depressive symptoms in adolescents in the Netherlands was equivalent to about \$235 million annually (Bodden et al., 2022). In

addition to the impairment associated with subclinical depressive symptoms on their own, research has noted that subclinical depressive symptoms predict the onset of *clinical* depression (Cuijpers et al., 2014; Garber & Weersing, 2010). Having an anxiety disorder diagnosis is also a risk factor for developing clinical depression; these disorders are highly comorbid, though anxiety typically occurs prior to the development of depression (Kalin, 2021). To prevent the development of clinical depression in children and adolescents, depressive symptoms should be intervened upon at the subclinical level. However, in order to be effective, the preventative intervention needs to be accessible, low-cost, and feasible without the use of clinician resources.

2.2.2 SYMPTOMS OF DEPRESSION AND ANXIETY ARE ASSOCIATED WITH DEFICITS IN COGNITIVE CONTROL.

Cognitive control involves the ability to direct attention towards regulating emotions and behaviors, and can be measured by tasks with a high cognitive demand (Joorman & Vanderlind, 2014; Muris et al., 2008). Accumulating evidence indicates that there are cognitive control behavioral deficits in youth with depression and anxiety (Han et al., 2016; Keller et al., 2019; Kertz et al., 2016), a dysfunction that is observed at the neurobiological level as well. For example, cognitive control is facilitated by a network of regions across superior parietal, lateral, and medial prefrontal cortex, sometimes referred to as the frontoparietal network (FPN; Zanto & Gazzaley, 2013). In youth with anxiety, as compared to healthy youth, there is hypo-*activity* of the FPN during cognitive control demanding tasks (Fitzgerald et al., 2013). Additionally, a meta-analysis of studies assessing major depressive disorder identified hypo-connectivity of the FPN as compared to healthy individuals (Kaiser et al., 2015). One model of depression in youth postulates that lower cognitive control capacity confers risk for developing depression; when challenging life events occur, those with lower cognitive control capacity are less able to implement effective emotional regulation, leading to worse symptoms (Joorman & Vanderlind, 2014; Tajik-Parvinchi et al., 2020). Despite evidence that targeting cognitive control might improve outcomes for youth with depression (Han et al., 2016), no preventative interventions for subclinical depression have been developed that specifically target cognitive control. The current project will assess a novel, low-cost and accessible preventative intervention that trains cognitive control, with the goal of reducing subclinical depression symptoms.

2.2.3 A VIDEO GAME (ENDEAVORRX) MIGHT IMPROVE COGNITIVE CONTROL AND THEREFORE REDUCE DEPRESSIVE SYMPTOMS

The intervention used in the current study is *EndeavorRx*, a video game that has been demonstrated to improve cognitive control in youth (Kollins et al., 2020). *EndeavorRx* is designed specifically to improve attention and cognitive control and is FDA approved to support the treatment of Attention-Deficit/Hyperactivity Disorder (ADHD; Davis et al., 2018; Kollins et al., 2020). In studies of ADHD-affected youth, the benefits of *EndeavorRx* on cognitive control appear to be maintained over time. Specifically, following *EndeavorRx* training, ADHD symptom reduction is maintained over a three year span (Jurigova et al., 2021). Though untested in youth with subclinical depressive symptoms, a recent study found that *EndeavorRx* led to improvements in cognitive control in adults with clinical depression (Keefe et al., 2022). Based on this convergence of evidence, we hypothesize that *EndeavorRx* will increase cognitive control and thereby reduce depressive symptoms in subclinically-affected youth. This hypothesis is further supported by preliminary work from our research group which demonstrated that an interactive-play cognitive training intervention in anxious preschoolers improved cognitive control and reduced anxiety symptoms (Schroder et al., 2022), which commonly precede depressive symptoms at later ages.

